12.2 Study Hypotheses

The primary endpoint is objective response in skin of at least 4 months duration (ORR4).

Response to cobomarsen will be compared to the control group using a Cochran-Mantel-Haenzel (CMH) statistic incorporating the stratification factors from the randomization.

The randomization will be stratified based on subjects with at least one skin tumor at Screening vs. no skin tumors at Screening. Subjects will also be stratified based on prognostic factors (age at diagnosis > 60 years and LDH level > ULN at diagnosis) (Scarlsbrick et al. 2015). Subjects will be stratified based on having 0-1 vs 2 of these prognostic factors.

There is only one primary and one key secondary endpoint (PFS) for analysis; a one-sided $p=0.025$ for response by CMH will establish statistical significance. The study hypothesis is that response to cobomarsen is superior to the control group. The null hypothesis (H_0) is that N (%) of responders to cobomarsen and N (%) of responders to control do not differ; the alternative hypothesis (H_a) is that N (%) of responders to cobomarsen is superior to N (%) of responders to control. A step-down procedure will be used to assess the statistical significance of PFS, such that a statistically significant difference in PFS will be confirmatory of a treatment effect only if the analysis of the primary endpoint is statistically significant at the one-sided 0.025 level of significance.

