12.4.4 Analysis of the Secondary Endpoints

The secondary endpoint of progression-free survival is defined as the time from randomization to the date of the earliest documented progression or death due to any cause.

Time to event analyses (Kaplan-Meier) will be done for PFS, time to \geq 50% mSWAT improvement, time to maximal effect in skin, duration of maintaining response in skin, CRR, and TTP. For responding subjects, duration of response and duration of \geq 50% improvement will be displayed.

Summary statistics for change from Baseline for mSWAT scores will be presented by treatment and visit.

The percent of subjects achieving $\geq 50\%$ improvement in mSWAT scores will be presented by treatment for:

- $\geq 50\%$ improvement for at least 28 days;
- $\geq 50\%$ improvement at 4 months;
- $\geq 50\%$ improvement at 28 days.

The N (%) of complete responses will be presented by treatment.

P-values generated from secondary analyses are supportive only. The mean change from baseline in use of pruritus medication will be presented by treatment and visit.

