12.5.2 Key Secondary Endpoint Sample Size

The null hypothesis is that there is no difference in progression free survival (PFS) between cobomarsen and vorinostat. A sample size of 126 subjects (63 per group; 66 events) provides at least 80% power to detect a difference between vorinostat and cobomarsen, assuming a median PFS of 4 months for vorinostat and 8 months for cobomarsen. This calculation is based on a one-sided, logrank test at the 0.025 level of significance, assuming 15 months of recruitment, 6 months of follow-up, and 17% censoring. No interim analysis is planned for PFS.

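### Section 12.4.4 calls secondary p-values supportive without excepting PFS, which 12.2 makes confirmatory after ORR4; the wording, and the 12.2 gate level, need aligning

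*Combined protocol and SAP*

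**What the plan says.** Three parts of section 12 bear on the status of PFS.

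- **12.2 Study Hypotheses:** "There is only one primary and one key secondary endpoint (PFS) for analysis". Under its step-down, "a statistically significant difference in PFS will be confirmatory of a treatment effect only if the analysis of the primary endpoint is statistically significant". The gate is set there at one-sided 0.025. The same section tests response with a CMH statistic that uses the randomization strata.
- **12.5.2 Key Secondary Endpoint Sample Size:** "The null hypothesis is that there is no difference in progression free survival (PFS) between cobomarsen and vorinostat". It assumes 126 subjects, 66 events, medians of 4 and 8 months, and at least 80% power. "This calculation is based on a one-sided, logrank test at the 0.025 level of significance", and "No interim analysis is planned for PFS".
- **12.4.4 Analysis of the Secondary Endpoints:** it opens with "The secondary endpoint of progression-free survival is defined as the time from randomization" and continues "Time to event analyses (Kaplan-Meier) will be done for PFS" and several other endpoints. Near its end it states "P-values generated from secondary analyses are supportive only", and it makes no exception for PFS.

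Two further places matter. Section 12.5.1 splits the primary's one-sided 0.025 into 0.01 at the interim and 0.015 at the final analysis. The synopsis (Statistical Methods) and 12.1 leave analysis detail to a SAP that is to be completed before database lock. The text reviewed contains no separate SAP section that settles the matter.

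**The concern.** PFS is the only endpoint besides ORR4 on which the plan allows a confirmatory claim. If both are significant, 12.2 supports that claim, while 12.4.4 taken at its word reduces the PFS p-value to supporting evidence. A plan should give one answer to what a significant PFS result establishes, particularly in an open-label trial where accumulating data may be visible before the database is locked.

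Two smaller matters sit beside this. The 12.2 gate is set at 0.025, although the primary is never tested at that level at either of its two analyses. The only PFS test named is in the sizing paragraph, and no section says whether it uses the randomization strata.

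**Working it through.** **1. The plan's own figure.** Inputs from 12.5.2: medians of 4 and 8 months (hazard ratio 0.5 under exponential PFS), one-sided 0.025, 80% power. Allocation is 1:1 (section 4.1).

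- Events = 4 × (1.960 + 0.842)² / (ln 0.5)² = 65.3, rounded up to 66.
- Power at 66 events = Φ(√66 × 0.6931/2 − 1.960) = Φ(0.856) = 80.4%.

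The stated 66 events and at least 80% power reproduce, for an unstratified log-rank test. The wording conflict changes neither.

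**2. The sections side by side, supposing ORR4 and PFS are both significant.**

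| Section | What it calls PFS | What a significant PFS result is |
|---|---|---|
| 12.2 | the one key secondary endpoint | confirmatory, by step-down |
| 12.5.2 | key secondary endpoint (section title) | outcome of a sized test at one-sided 0.025 |
| 12.4.4 | a secondary endpoint | supportive, if the closing sentence covers it |

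Nothing in 12.4.4 limits that sentence to the other endpoints, and PFS is the first endpoint the section names.

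**3. The gate.** Suppose the final primary p-value lies between 0.015 and 0.025. Section 12.2 as worded opens the PFS test, but under 12.5.1 the primary has not met its final level. The gate should use the level that the primary test actually has.

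**4. Stratifying the PFS test (optional).** The documents give neither the prevalence nor the prognostic strength of the two factors, so the following rests on assumptions. Simulation: 126 subjects, permuted blocks of 4 within four strata, true hazard ratio 0.5, overall control median 4 months, 15 months of uniform accrual, and exponential dropout of 0.031 per month. That dropout rate loses 17% of subjects, which is one reading of the 17% censoring in 12.5.2, and gives 84.2 expected events at month 21. Assumed prevalences (tumors / two prognostic factors) are 20/10%, 35/15% and 50/25%, with the factors independent.

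Change in power from stratifying, in points, in that order:

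| Assumed HR per factor | At 66 events | At month 21 |
|---|---|---|
| 1 (not prognostic) | −1.54, −1.73, −1.75 | −1.14, −1.32, −1.58 |
| 1.5 | −0.80, −0.19, −0.36 | −0.62, −0.17, +0.21 |
| 2 | +1.30, +2.12, +3.26 | +1.44, +2.43, +3.71 |

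With non-prognostic factors, power at exactly 66 events is 79.2–79.6% unstratified and 77.4–78.0% stratified. At month 21 it is 88.4–88.6% and 87.0–87.3%. The two tests disagree on significance in 3–5% of trials if the factors are not prognostic, and in 5–8% at HR 2 each. One-sided type I error at 66 events is 2.4–2.7% stratified and 1.9–2.7% unstratified. The smallest stratum considered expects 126 × 0.20 × 0.10 = 2.5 subjects, and the loss there (1.1–1.5 points) is no larger than with bigger strata.

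**The case against.** The strongest reply is that a specific rule governs a general sentence. Section 12.2 sets out the step-down explicitly, and 12.5.2 gives PFS a null hypothesis, test, side, level, event count and no-interim rule. Against these stands one generic sentence placed between the response percentages and pruritus medication, which a fair reader would take to mean the other secondaries. That largely stands: 12.2 is probably what is intended, and this is a drafting slip. The text still does not say so, and the repair is a few words.

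Four stronger readings are tempting and are not supported:

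- **That PFS status would have to be settled after the data are seen.** The SAP is due before database lock and could settle it first. What remains is that open-label data may be visible by then, and that a SAP would leave the conflicting sentence in the protocol.
- **That 3.2.2 adds to the conflict by listing PFS without a key label.** An endpoint list need not repeat the testing hierarchy, which 12.2 and 12.5.2 supply.
- **That no PFS test is specified.** Section 12.5.2 names a one-sided log-rank test at 0.025; it is only missing from the analysis section.
- **That omitting the strata is an error.** Nothing in the plan requires a stratified PFS test, the SAP may specify one, and the unstratified test does not inflate type I error.

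It can also be said that the figures above do not favour stratifying unless the factors are clearly prognostic for PFS. That is correct, and it is why stratification is offered as an option only.

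**Conclusion.** The conflict is real and one of wording. Read literally, 12.4.4 withdraws the confirmatory PFS claim that 12.2 allows. It decides what a significant PFS result may establish, and it alters no sample size, event count or alpha. This follows from the text alone and needs no numerical assumption.

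The 12.2 gate level is a related mismatch with 12.5.1 and should be settled in the same edit.

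Stratifying the PFS test is a matter of efficiency: a loss of about 1 to 2 points if the factors are not prognostic, close to neutral at HR 1.5 each (−0.8 to +0.2), and a gain of about 1 to 4 points at HR 2 each. Those sizes depend on the assumed prevalences, hazard ratios and dropout model.

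**What to change.** 1. In 12.4.4, replace the sentence with: *P-values from secondary analyses other than PFS are supportive only; PFS is tested under the step-down in 12.2 by a one-sided log-rank test at the 0.025 level.*
2. In 12.2, make the gate refer to the primary test being significant at its allocated level (one-sided 0.01 at the interim or 0.015 at the final analysis, as in 12.5.1) in place of 0.025. PFS is tested once, with no interim, so it keeps its own 0.025.
3. Optional: stratify the PFS log-rank test by the two randomization factors (skin tumor or none; 0–1 or 2 prognostic factors), as the primary CMH test already is, with a stratified Cox hazard ratio and confidence interval. If this is adopted, 12.5.2 should say that its 80% at 66 events is the unstratified formula value; simulated power for the stratified test at exactly 66 events is about 77–78% if the factors are not prognostic. If an unstratified test is preferred, saying so is enough.

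Items 1 and 2 cost a sentence each and need no new data. Item 3 costs the 1 to 2 points of PFS power given above if the factors turn out not to be prognostic.

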12.4.5 Safety Analyses

Treatment-emergent AEs will be coded by preferred term and system organ class using the Medical Dictionary for Regulatory Activities (MedDRA[®]) and summary tables for all AEs will be generated for the Safety Population. Incidence rates and percentages will be summarized by preferred term and system organ class. Additional summary tables will be generated for the following population subsets: subjects with SAEs, subjects with treatment related AEs, subjects who discontinue due to AEs, and subjects with grade 3 or 4 AEs. Severity will be assessed according to the NCI CTCAE version 5.0 and relationship to study treatment will be attributed by investigator.

Concomitant medications will be coded using the World Health Organization Drug Dictionary (WHO-DD; March 2015 or later version). A dictionary listing of all unique concomitant medications used in the study will be provided.

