4.1 Randomized Period

Approximately 126 subjects are expected to be enrolled. An interim analysis will be conducted after approximately 40 subjects have been followed for a minimum of approximately 6 months; enrollment will be suspended after approximately 40 subjects have been enrolled until the completion of the interim analysis.

Subjects will be randomized in a 1:1 ratio to receive cobomarsen or vorinostat. Subjects will undergo Screening lasting up to 28 days from the time of informed consent, followed by active treatment, and then follow-up for response and disease progression.

Figure 1. SOLAR Study Design Schematic

Subjects will remain on their assigned study treatment until one of the following occurs:

1. Disease progression, defined as either (see [Appendix F](#)):
 - a. Confirmed progression in skin
 - b. Clinical progression in other compartments, documented by assessments (flow cytometry and/or CT scan) completed per investigator discretion
 - c. Partial or complete skin response followed by a confirmed loss of skin response as defined by an increase of mSWAT of greater than the sum of nadir plus 50% baseline score.

Progressions based on mSWAT will be confirmed by repeated measurement 28 days (± 3 days) after the first determination of progression.

If confirmed, the date of progression will be based on the first determination of progression. Subjects will continue the study treatment until disease progression is confirmed.

2. Subject meets one of the other treatment discontinuation criteria (see [Section 5.4.1](#)).

Safety assessments will include monitoring the incidence and severity of AEs and SAEs, physical examination findings, vital signs, ECG monitoring, and clinical laboratory assessments.

Samples will be collected for PK in the cobomarsen group on Days 1, 2, 3, 5, 8, 15, 29, and every 4 weeks from Weeks 9 through 81, every 8 weeks thereafter, and at the follow-up/end of treatment visit.

mSWAT evaluations will be completed on Days 1 and 29, every 4 weeks through Week 81, every 8 weeks thereafter, and at the End of Treatment and Follow-up visits. Every effort will be made to perform a final disease assessment for subjects who withdraw from the study early.

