12.4.5.2 Physical Examination

Clinically significant changes in vital signs and clinically significant findings on physical examination will be recorded as AEs. Incidence of subjects with changes from normal physical examination findings at baseline to abnormal during the study may be generated.

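### Section 12.4.5 sets no denominator, time window or exposure summary for adverse events, although AE observation follows progression and would run longer on cobomarsen under the plan's own PFS assumption

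*Combined protocol and SAP*

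**What the plan says.** The AE analysis is in protocol Section 12.4.5. Treatment-emergent AEs are coded and tabulated for the Safety set: "Incidence rates and percentages will be summarized by preferred term and system organ class". Further tables cover subjects with SAEs, treatment-related AEs, AEs leading to discontinuation, and grade 3 or 4 AEs. Section 12.4 contains no person-time denominator, common time window, time-to-first-AE analysis or summary of treatment duration.

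Three other places determine how long each subject is observed:

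- **Treatment duration.** Section 4.1: "Subjects will remain on their assigned study treatment until one of the following occurs". The events listed are progression and the other stopping criteria of Section 5.4.1. Treatment continues until skin progression is confirmed about 28 days later.
- **AE window.** Sections 7.2.1 and 10.5.1 collect AEs of any cause from consent to 60 days after the last dose. Only treatment-related AEs are reported beyond that.
- **Planned effect.** Section 12.5.2 sizes PFS "assuming a median PFS of 4 months for vorinostat and 8 months for cobomarsen".

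Sections 12.3.2 and 12.4.5 do not say where AEs are counted once a vorinostat subject has crossed over to cobomarsen.

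**The concern.** AE observation ends with treatment, not on a common date, and treatment ends mainly with progression. If cobomarsen delays progression as planned, its subjects are watched for longer. A crude percentage then mixes toxicity per unit time with duration of benefit, to the disadvantage of the drug that works longer. Section 4 describes the trial as assessing efficacy and safety against vorinostat, and readers will set the two columns side by side even though no test is planned.

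The wording does not settle the matter. The term used in Section 12.4.5 could mean a person-time rate, but no unit is given. Section 12.4.5.2 uses the related word for a count of subjects: "Incidence of subjects with changes from normal physical examination findings at baseline to abnormal during the study".

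Crossover adds a second ambiguity. A subject can start cobomarsen within 60 days of the last vorinostat dose, so one AE can fall into both windows.

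**Working it through.** **1. The plan's own figure.** Inputs from Section 12.5.2: medians of 4 and 8 months (hazard ratio 0.5 if exponential), "one-sided, logrank test at the 0.025 level of significance", 80% power; 1:1 allocation from Section 4.1. Schoenfeld's formula gives 4 × (1.960 + 0.842)² / (ln 2)² = 4 × 7.85 / 0.480 = 65.3, so 66 events, and power at 66 events is 80.4%. This matches "A sample size of 126 subjects (63 per group; 66 events) provides at least 80% power". The medians are therefore the working assumptions of the design.

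**2. Time under observation.** Assume exponential time to progression, treatment to progression, and a 60-day (about 2-month) tail. The progression hazard m is ln 2/4 = 0.1733 per month on vorinostat and ln 2/8 = 0.0866 on cobomarsen. Mean time to progression is 1/m.

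| Setting | Vorinostat, months | Cobomarsen, months | Ratio |
|---|---|---|---|
| Time to progression, no limit | 5.8 | 11.5 | 2.00 |
| Same + 60-day tail | 7.8 | 13.5 | 1.74 |
| 36-month cap (from Section 10.10) + tail | 7.7 | 13.0 | 1.68 |
| Calendar cut, 15 months' uniform accrual + 6 (5.0 v 7.7) + tail | 7.0 | 9.7 | 1.38 |
| 36-month cap + tail, 3% per month stop for other reasons | 6.9 | 10.4 | 1.51 |
| 36-month cap + tail, 10% per month stop for other reasons | 5.6 | 7.3 | 1.30 |

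The calendar cut uses "assuming 15 months of recruitment, 6 months of follow-up, and 17% censoring" for its 15 and 6 months. The other-reason stopping rates are assumptions, because the plan gives none.

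**3. Crude percentage at equal toxicity.** Let L be a constant AE hazard per month, the same in both arms, and g the hazard of stopping for other reasons. With no data cut, the share of subjects with the event is

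P = 1 − exp(−2L) × (m + g) / (L + m + g).

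- L = 0.05, g = 0: 1 − 0.9048 × 0.1733/0.2233 = 0.298, against 1 − 0.9048 × 0.0866/0.1366 = 0.426. That is 30% v 43%, ratio 1.43.
- L = 0.02, g = 0: 0.139 v 0.219, or 14% v 22%, ratio 1.58.
- L = 0.05, g = 0.03: 1 − 0.9048 × 0.2033/0.2533 = 0.274, against 1 − 0.9048 × 0.1166/0.1666 = 0.367. That is 27% v 37%.
- L = 0.05, g = 0.10: 1 − 0.9048 × 0.2733/0.3233 = 0.235, against 1 − 0.9048 × 0.1866/0.2366 = 0.286. That is 24% v 29%.

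Anchored instead on a vorinostat percentage of 20% with the tail included, cobomarsen shows 30.1% with the 36-month cap and 26.4% at the calendar cut.

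**4. What a first-event rate does.** Mean time at risk to first event is P/L: 0.298/0.05 = 5.96 months and 0.426/0.05 = 8.53 months. Dividing P by it returns 5 per 100 patient-months in both arms, a ratio of 1.0.

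**5. Early AEs.** If the AE can occur only in the first month on treatment, 20% on vorinostat becomes 20.8% on cobomarsen, so the percentages are nearly right. A person-time rate now misleads the other way. Take 20% in each arm, with events at about half a month and the 36-month-cap observation times. Time at risk per subject is 0.8 × 7.7 + 0.2 × 0.5 = 6.3 months, against 0.8 × 13.0 + 0.2 × 0.5 = 10.5. The rates are 20/6.3 = 3.2 and 20/10.5 = 1.9 per 100 patient-months, which flatters cobomarsen.

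**The case against.** Several points on the other side are sound.

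- **The safety objective names no comparator.** Section 3.1.2 concerns the safety of cobomarsen in MF. Comparative wording appears only in Sections 2.2 and 4, and Section 12.4.5 plans descriptive tables without a test. A reader might infer that safety relative to vorinostat is itself a secondary objective; the text does not say so.
- **The wording is ambiguous rather than plainly crude.** The term in Section 12.4.5 does not exclude person-time rates. What stands is that it is undefined.
- **Detail is deferred.** Section 12.1 leaves methods to a SAP due before database lock. The supplied text contains no such detail, so the gap is open but could be closed there.
- **Time on drug is not PFS.** A reader might infer that the plan assumes twice the time on cobomarsen. It states no exposure figure. The factor of two is the ratio of median PFS, and Section 5.4.1 lists many other reasons to stop treatment, after which subjects may be followed for progression while off drug.
- **Person-time rates have their own bias**, as step 5 shows. They should not displace the percentages.

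None of these removes the direction of the effect for AEs that accrue over time.

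**Conclusion.** The concern holds as a gap in the specification with a foreseeable direction. Under the planned PFS medians and treatment to progression, AE observation would be about 1.4 to 1.7 times as long on cobomarsen, falling to 1.3 if 10% per month stop for other reasons. For AEs accruing at an equal constant hazard of 5% per month, the crude excess on cobomarsen runs from 13 percentage points (30% v 43%, no other stopping and no cut) down to 5 (24% v 29%).

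These figures rest on exponential progression times, a constant AE hazard equal in both arms, and assumed rates of other stopping. They also require cobomarsen to work as planned; with no PFS difference and equal stopping, the artefact disappears.

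The broad claim that equal toxicity would always look clearly worse on cobomarsen is not supported. It fails for early-onset AEs, and Section 2.3.1 links constitutional symptoms mainly to initial doses. No primary or key secondary inference is touched. The change is still worth making, because it is cheap and the trial is open-label, so it is best fixed before results accumulate.

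**What to change.** Define the term for incidence rates in Section 12.4.5 and keep the crude percentages. For all TEAEs, grade 3–4 AEs, SAEs and AEs of special interest, add:

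1. A summary by arm of treatment duration and AE observation time.
2. Exposure-adjusted incidence rates: subjects with a first event per 100 patient-months at risk. Time runs from first dose to the earliest of first event, last dose + 60 days, or first crossover dose.
3. Cumulative incidence of first event by Week 17, a scheduled visit in both arms close to the assumed vorinostat median. State one rule for the end of AE observation, for example death as a competing event and all other ends of observation censored.

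Tabulate AEs after the first crossover dose separately from the vorinostat arm.

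The cost is a few extra tables from dosing and AE dates already collected; no visit or procedure changes. The downside is in interpretation: person-time rates understate early-onset AEs in the arm with longer exposure, so they must be read beside the Week 17 figures.
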